The purpose of this study is to examine the impact of an OA-specific aerobic and strengthening exercise program, delivered within the workplace, on mobility, pain, physical capacity, and resilience among workers with knee or hip OA as well as those with no joint pain. We hypothesize that exercise designed for OA, delivered at work, will improve all of these outcomes.

METHODOLOGY

Participants

Participants will be women and men employed in administrative roles at Ford Motor Company in Oakville. All eligible participants will be welcome to participate.

Inclusion and Exclusion Criteria: We will recruit 40 participants from Ford. Inclusion criteria include part- or full-time employment in an administrative role at Ford. Men and women will be welcome. The exclusion criteria include a self-reported history of patellofemoral symptoms because the exercise program delivered to the intervention group places large loads on this joint. Participants with a previous osteoporotic fragility fracture will be excluded. Those with osteoporosis but no fragility fracture will be eligible. Exclusion criteria include active non-arthritis joint disease (e.g., gout); conditions that might be exacerbated (e.g., unstable angina); neurological conditions such as a stroke; leg trauma within 3 months; and cancer. Participants will be screened for the American College of

Rheumatology (ACR) criteria for clinical knee or hip OA. However, participants not meeting this criterion will still be eligible to participate.

Recruitment & Sample Size: Participants will be recruited through the research coordinator at McMaster. Administrative personnel at Ford who are not in a supervisory role (i.e., Fitness Centre Manager) will disseminate recruitment posters and an email/verbal script. Both will request that interested employees directly contact the research coordinator. These materials will explicitly state that the decision to participate, or not participate, will not be shared with Ford administration.

Our primary outcome is change in self-reported mobility on the Lower Extremity Functional Scale (LEFS). Self-reported mobility is critically important from the patient's perspective ¹³ and is likely to see the largest effect of exercise ¹⁴. The minimal clinically important difference (MCID) of the LEFS is 5 points ^{15, 16}. Rehabilitation produces changes of ≥ 10 LEFS points, with an effect size of 0.5¹⁷. Given a Type I error=0.05 on change, n=27 will yield 81% power.

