Randomization: An independent research assistant will conduct randomization and concealed allocation. Participants will be randomized to receive either the exercise intervention, or no intervention. After baseline, the independent research assistant will provide each participant with one sequentially numbered, sealed, opaque envelope that identifies the intervention they will receive.

Interventions

Exercise Program: A 12-week exercise intervention will be offered in the workplace. Ford employees will complete their exercise program at Ford in the on-site exercise facility. 20 of the 40 participants will be randomized to the exercise intervention.

A 12-week supervised exercise program designed for OA knees and hips will emphasize strengthening leg muscles with minimal loads. Each exercise program will be 30 minutes and offered at 7:00am (Mon, Tues, Wed, Thurs, Fri). These timeslots will enable participants to exercise at the start of their workday. Participants will be asked to attend 3 or more supervised exercise sessions weekly ¹⁸. Strengthening will focus on "body weight" strategies that we have used previously, such as squats and lunges. A certified yoga instructor will offer exercise modifications and education about anatomy, OA, and proper lower limb alignment. Over 12 weeks, the exercises will be progressed. These exercises yield nominal loads while increasing leg strength ¹⁹. Our previous randomized controlled trial of this intervention (n=31), delivered within the community, yielded improvements in pain, mobility and self-reported physical function without adverse events.

Control Program: 20 of the 40 participants will be randomized to the control group. These participants will be asked to refrain from changing any interventions or activity existing at baseline over the 12-week intervention period. Afterwards, these participants will be offered the same exercise program free of charge.

Outcome Measures

Outcome measures will be collected at baseline and immediately after the 12-week exercise program.

Primary Outcome: The primary outcome is the change between baseline and follow-up on the LEFS ^{16, 20, 21}. The LEFS consists of 20 items on an adjectival scale that assess difficulty during mobility tasks ranging from transfers to running. This range avoids ceiling and floor effects. It is reliable and valid in OA and has superior sensitivity to change compared to similar measures ^{17, 21, 22}.

Secondary Outcomes

- *Pain:*

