 - The Work Ability Index (WAI) is a widely-used self-report questionnaire that consists of seven dimensions including current work ability relative to life-time best, work ability related to job demands, number of current physician-diagnosed health conditions, estimated work impairment due to the conditions, sick leave over the past year, own prognosis, and mental resources ³⁹. The WAI produces reliable data ³⁹.
 - Depressive symptoms will be assessed with the Center for Epidemiologic Studies—Depression (CES-D) Scale, a 20-item scale with emphasis on affect (mood, guilt, worthlessness, helplessness, appetite) ⁴⁰. Data from the CES-D are valid and reliable in adult and arthritic populations ⁴⁰⁻⁴².
 - Self-efficacy will be measured using the Arthritis Self-Efficacy Scale (ASES). The ASES measures arthritis-specific beliefs regarding perception of performance on certain tasks to cope with the disease ⁴³. The ASES produces both reliable and valid data in knee OA ⁴⁴.

Statistical Analyses: Descriptive statistics will be calculated. A repeated measures analysis of variance will be used to compare the impact of the exercise program on change scores for each outcome measure between the exercise and control groups. Independent analyses will be performed for participants that demonstrated clinical criteria for hip and knee OA.

References

1. Canada S. Population by sex and age group. 2013; <http://www.statcan.gc.ca/tables-tableaux/sum-som/l01/cst01/demo10a-eng.htm>. Available at. Accessed May 15 2014, 2014.
4. Canada AAo. *The impact of arthritis in Canada: Today and over the next 30 years*. 2011.

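### Is it a flaw that the pooled LEFS comparison has no term for osteoarthritis status?

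*Combined protocol and SAP*

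**What the plan says.** The sample is mixed by design. Under Inclusion and Exclusion Criteria, "Participants will be screened for the American College of" Rheumatology clinical criteria for knee or hip OA, and then: "However, participants not meeting this criterion will still be eligible to participate". The expected share with OA is not stated.

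Under Interventions, "20 of the 40 participants will be randomized to the exercise intervention", and the other 20 go to control. The Randomization paragraph describes concealed allocation ("After baseline, the independent research assistant will provide each participant with one sequentially numbered, sealed, opaque envelope") and names no stratification factor.

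Under Outcome Measures, "The primary outcome is the change between baseline and follow-up on the LEFS". The Statistical Analyses paragraph will "compare the impact of the exercise program on change scores for each outcome measure between the exercise and control groups", with no covariate named, and continues: "Independent analyses will be performed for participants that demonstrated clinical criteria for hip and knee OA".

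**The concern.** The protocol itself treats OA as important. The exercise programme was designed for OA joints, every participant is classified at screening, and OA gets its own analysis. Yet the pooled LEFS comparison, which carries the primary result, does not use the classification.

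With 40 people and no stratification, the arms could by chance hold different numbers of OA participants. If OA status also predicts LEFS change, two things would be at stake. An imbalance would move the observed difference between arms, and variation attributable to OA would stay in the error term and cost precision. One extra factor, at one degree of freedom and with no new data, looks like a cheap remedy for both.

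**Working it through.** **Inputs from the document.** 20 per arm; MCID 5 LEFS points; rehabilitation changes of at least 10 points with an effect size of 0.5 (Recruitment & Sample Size); two-arm comparison of change.

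**Assumptions, because the document gives no values.** OA share p; SD of LEFS change; g, the OA v non-OA difference in change without exercise; h, the extra gain from exercise in OA. Reading 10 points and 0.5 as 10/SD gives SD = 20. The document does not say which SD underlies the effect size, so SD = 10 is shown too.

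**The plan's own figure.** The protocol states: "Given a Type I error=0.05 on change, n=27 will yield 81% power". A one-sample (paired) t-test on change with n = 27, effect 0.5 and one-sided 0.05 gives 81.2%, so the figure reproduces on that basis. It is not the between-arm comparison, so the comparison below uses a two-sample noncentral t with 20 per arm and two-sided 0.05.

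**Step 1. Validity.** Randomization makes the unadjusted contrast unbiased over allocations. Its standard error is SD × √(1/20 + 1/20): 20 × 0.316 = 6.3 points, or 10 × 0.316 = 3.2 points. Chance differences in OA counts are part of the variation this standard error describes.

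**Step 2. Chance imbalance.** The number with OA is taken as binomial(40, p), and the split between arms as hypergeometric.

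| OA share | arms differ by 4 or more | arms differ by 6 or more |
|---|---|---|
| 10% | 6.3% | 0.4% |
| 20% | 16.4% | 2.9% |
| 40% | 25.8% | 7.5% |

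For an OA count difference d, the unadjusted contrast shifts by g·d/20 + h·d/40.

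- g = 0, h = 5–10: 0.5–1.0 point at 10 v 6 (d = 4) and 0.75–1.5 points at 11 v 5 (d = 6).
- g = 5, h = 5–10: 1.5–2.0 and 2.25–3.0 points.

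The largest, 3.0 points, is 3.0/6.3 = 0.47 standard error at SD 20 and 3.0/3.2 = 0.95 at SD 10. It needs both the less common imbalance and g = 5.

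**Step 3. Cost of the term.** The arm variance is multiplied by 1/(1 − r²), where r is the correlation of arm with OA: 1.043 at 10 v 6, 1.103 at 11 v 5, and 1.028 on average over allocations. The error df falls from 38 to 37.

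**Step 4. Power at effect 0.5.** Without the term it is 33.8%. With it, averaged over allocations:

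| Share of LEFS-change variance explained by OA (R²) | Power |
|---|---|
| 0 | 33.0% |
| 0.05 | 34.5% |
| 0.10 | 36.1% |
| 0.20 | 39.7% |

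The term breaks even at R² of about 0.027.

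**Step 5. Which R² is plausible?** R² = (g + h/2)² · p(1 − p)/SD², with p = 0.4 (16 of 40):

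| g | h | SD | R² | Power with term |
|---|---|---|---|---|
| 0 | 5 | 20 | 0.004 | 33.1% |
| 0 | 10 | 20 | 0.015 | 33.4% |
| 5 | 5 | 20 | 0.034 | 34.0% |
| 5 | 10 | 20 | 0.06 | 34.8% |
| 0 | 5 | 10 | 0.015 | 33.4% |
| 0 | 10 | 10 | 0.06 | 34.8% |
| 5 | 5 | 10 | 0.135 | 37.3% |
| 5 | 10 | 10 | 0.24 | 41.4% |

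At SD 20 and g = 0 the term loses 0.4–0.7 point of power. At SD 20 and g = 5 it gains 0.2–1.0 point. Gains above 1 point in this grid need SD 10 and g = 5 together. But g = 5 means that unexercised OA and non-OA participants differ in 12-week change by the whole MCID, in a control group asked to keep its interventions and activity as they were at baseline. Nothing in the document supports that value.

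**The case for a change.** The strongest case for the term is that the trade looks lopsided. If OA explains nothing, average power falls by only 33.8 − 33.0 = 0.8 point. If OA explains 10% or 20% of the variance, power rises by 2.3 or 5.9 points. An OA main effect would also remove nearly all of the shift from an imbalance, leaving at most about 0.1 point at 10 v 6 and 0.2 at 11 v 5. And naming the term in advance would prevent a decision to adjust being taken after an imbalance has been seen.

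Some of this stands. The pooled model does omit OA, the variable is available, and prespecifying any adjustment is better than choosing it afterwards. A team with good reason to think OA strongly predicts LEFS change could sensibly include it.

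What does not stand is the step from there to a deficiency. The upside depends on R² values that the document does not support, while on the SD 20 reading without a prognostic difference the expected result is a small loss. Even the small cost is an average: at 11 v 5 with R² = 0, power falls to 31.1%. Nor is OA status the obvious covariate. Baseline LEFS is also measured before allocation and is the more usual adjuster for a LEFS change outcome, and nothing shows that a yes/no OA flag would add to it. OA status is not wasted either, since the separate OA analysis uses it.

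**Conclusion.** The concern does not hold. The planned pooled comparison is a valid, unbiased randomized contrast, and whether to spend one of 38 error degrees of freedom on an unstratified binary factor of unknown prognostic value is a matter on which statisticians may reasonably differ.

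The size of the issue is a change in power from −0.8 to +5.9 points around 33.8%, for R² from 0 to 0.20. On the SD 20 reading with 40% OA it narrows to between −0.7 and +1.0 point, and is negative unless OA predicts change without exercise. These figures rest on assumed values for the OA share, SD, g and h, and on 20 analysed per arm.

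The gap between the stated 81% and the 33.8% for the two-arm comparison is a separate question about the sample-size basis. An OA term would not close it, and its absence did not cause it.
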